Appendix I

Table 1. Censoring rules for PFS

Situation	Date of progression or censoring	Outcome
Progression documented between scheduled visits	Earliest of: 
• Date of radiological assessment showing new lesion (if progression is based on new lesion); or• Date of last radiological assessment of measured lesions (if progression is based on increase in sum of measured lesions); Or	Progressed
Death before first progression disease assessment	Date of death	Progressed
Death between adequate assessment visits	Date of death	Progressed
No progression	Date of last radiological assessment of measured lesions	Censored
Treatment discontinuation for undocumented progression	Date of last radiological assessment of measured lesions	Censored
Treatment discontinuation for toxicity or other reason*	Date of last radiological assessment of measured lesions	Censored
Death or progression after more than one missed visit *	Date of last radiological assessment of measured lesions	Censored

* In accordance with these criteria death after the end of treatment visit will be considered as censored with the date of last radiological assessment of measured lesions.

Table 2. Censoring rules for PFS as assessed by investigator.

Situation	Date of progression or censoring	Outcome
No baseline assessment	Randomization + 1 day	Censored
Progression documented* between scheduled visits	Next scheduled visit	Progressed
No progression	Date of last visit with adequate assessment	Censored
Investigator's claim of progression*	Scheduled visit (or next scheduled visit if between visits)	Progressed
Treatment discontinuation for toxicity or other reason **	Date of last visit with adequate assessment	Censored
New anticancer treatment started with no claim of progression	Date of last visit with adequate assessment	Censored
Death before first progression disease assessment	Date of death	Progressed
Death between adequate assessment visits	Date of death	Progressed
Death after an extended lost-to-followup time (two or more missed assessments)**	Last visit with adequate assessment	Censored

* In addition to the progressions confirmed by radiological criteria, also the progressions evaluated by the investigator, without a radiological image confirming them, will be considered as PFS events.

** In accordance with these criteria death after the end of treatment visit will be considered as censored with the date of last adequate assessment.

Table 3. Censoring rules for OS

Situation	Date of death or censoring	Outcome
Death during study follow-up	Date of death	Death
The patient is alive at last follow-up	Date of last follow-up	Censored

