Participants who are eligible to receive retreatment with pembrolizumab according to the criteria in Section 5.3.5 will move to the Second Course Phase when they experience disease progression. The same visits and evaluation calendar of the First Course will be followed during the Second Course Phase.

Follow-up visits

A follow up visit is required as per protocol to be performed to patients that finish the First Course Phase and are candidates to enter to the Second Course Phase of re-treatment with pembrolizumab, once disease progression is confirmed. A eCRF page will have to be completed in order to confirm the progression date. The tumor evaluation performed to confirm the progression disease before entering the Second Course Treatment will also be recorded at the eCRF.

During the period between the First and Second Course phases, it is highly recommended to perform safety follow up visits every 6 weeks and efficacy assessments every 12 weeks. However, patient's follow up during this period will be done as per local practice and at the Investigator criteria.

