6.4.3 OS and PFS definitions

OS is defined as the time from first dose of study treatment to death due to any cause. Subjects without documented death at the time of the final analysis will be censored at the date of the last follow-up.

PFS is defined as the time from first dose of study treatment to the first documented disease progression based on RECIST v.1.1 or death due to any cause, whichever occurs first.

6.4.4 irRECIST

Immunotherapeutic agents such as MK3475 (pembrolizumab) may induce antitumor effects by potentiating endogenous cancer-specific immune responses. The response patterns observed with these compounds may be different to the typical time course of responses seen with classical cytotoxic agents, and can manifest a clinical response after an initial increase in tumor burden or even the appearance of new lesions. Standard RECIST v.1.1 may, therefore, not provide a precise response assessment of immunotherapeutic agents such as MK3475 (pembrolizumab) .

irRECIST is RECIST v.1.1 adapted to account for the unique tumor response seen with immunotherapeutic agents. In this way, in subjects who have initial evidence of radiological disease progression by RECIST v.1.1, it is at the discretion of the Investigator whether to continue a subject on study treatment until repeat imaging is obtained. Subjects may receive study treatment and tumor assessment should be repeated at least four weeks later in order to confirm disease progression by irRECIST. Any subject deemed clinically unstable should be discontinued from trial treatment at first radiologic evidence of disease progression and is not required to have repeat imaging for disease progression confirmation. Clinical stability is defined as the following:

- Absence of symptoms and signs indicating clinically significant disease progression, including worsening of laboratory values.

- No decline in ECOG performance status.
- Absence of rapid progression of disease.
- Absence of progressive tumor at critical anatomical sites (e.g., cord compression) requiring urgent alternative medical intervention.

In determining whether or not the tumor burden has increased or decreased per irRECIST, the local site Investigator should consider all target and non-target lesions as well as any incremental new lesion(s). Scenarios where disease progression is confirmed at repeat imaging if any of the following occur by irRECIST:

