- Tumor burden remains $\geq 20\%$ and at least 5 mm absolute increase compared to nadir.
- Non-target disease resulting in initial disease progression is worse (qualitative assessment).
- New lesion resulting in initial disease progression is worse (qualitative assessment).
- Additional new lesion(s) since last evaluation.
- Additional new non-target progression since last evaluation.

If repeat imaging confirms disease progression due to any of the scenarios listed above, subjects will be discontinued from study therapy. If repeat imaging does not confirm disease progression by irRECIST and the subject continues to be clinically stable, treatment may continue and follow the regular imaging schedule.

*Note: If a subject with confirmed radiographic progression per irRECIST, but the subject is achieving a clinically meaningful benefit, and there is no further increase in the tumor burden at the confirmatory tumor imaging, an exception to continue treatment may be considered following consultation with the Sponsor. In this case, if treatment is continued, tumor imaging should continue to be performed following the intervals as outlined in **Appendix 1**.*

*Note: In subjects who discontinue study treatment without documented disease progression, every effort should be made to continue monitoring their disease status by tumor imaging following the intervals as outlined in **Appendix 1** until the start of new anti-cancer treatment, disease progression, death, or the end of the study, whichever occurs first.*

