--	---------------------------------------------------------------------------------------------------------------------------------------------------------------------------------------------------------------------------------------------------------------------------------------------------------------------------------------------------------------------------------------------------------------------------------------------------------------------------------------------------------------------------------------------------------------------------------------------------------------------------------------------------------------------------------------------------------------------------------------------------------------------------------------------------------------------------------------------------------------------------------------------------------------------------------------------------------------------------------------------------------------------------------------------------------------------------------------------------------------

Exploratory objectives:

	  
	          
Design	Multicenter, open-label, phase II clinical trial.
Primary endpoint	The primary endpoint of this study is to assess the CBR based on RECIST v.1.1.
Study population and total number of subjects	Female patients age \geq 18 years with advanced HR-positive/HER2-negative breast cancer previously treated with anthracyclines and taxanes. A total of 44 patients will be enrolled into this trial.
Approximate duration of subject participation	All eligible patients will be treated with MK3475 (pembrolizumab) 200 mg on day 1 of each 21-day cycle and eribulin 1.23 mg/m ² (equivalent to eribulin mesylate at 1.4 mg/m ²) on days 1 and 8 of every 21-day cycle. Treatment with MK3475 (pembrolizumab) and eribulin will continue based on physician criteria. No maximum duration of treatment is specified. Study follow-up will be performed 12 months after last study dose.
Calendar and estimated completion dates	Recruitment period is planned to be opened for 11 months. The end of study will be 12 months after last study dose or progressive disease experienced in all patients or when the

	
trial is terminated by the Sponsor, whichever is earlier. This data point will be considered:
 
• End of Recruitment (LPI) (11 months): August 2018• Last Patient Last Visit (LPLV): August 2019• Final Study Report: December 2019

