6.2.1 Summary statistics

Efficacy:

- CBR is defined as the number of subjects with complete response (CR), partial response (PR) or stable disease (SD) for at least 24 weeks based on RECIST v.1.1 divided by the number of patients in the analysis set (in subjects with PD-L1 positive tumors). Tumor response will be defined as best response. The CBR results will be presented as number and proportion of patients with clinical benefit and 95% CI of the proportion.
- The radiological PFS is defined as the time from the first dose of treatment until death by any cause or objective tumor progression according to RECIST v.1.1. Patients with

EudraCT number: 2016-004513-27

no progression or death will be censored at the date of their last evaluable imaging.

PFS censoring rules will follow FDA guidance in 2007 (see Table 1 - Appendix I).

- The first dose of treatment is defined as the minimum date of the first administration of eribulin and/or pembrolizumab.
- The PFS as assessed by investigator is defined as the time from the first dose of treatment until death by any cause or objective tumor progression as assessed by investigator according to RECIST v.1.1. Patients with no progression or death will be censored at the date of their last evaluable imaging. PFS censoring rules will follow FDA guidance in 2007 (see Table 2- Appendix I).
 - The first dose of treatment is defined as the minimum date of the first administration of eribulin and/or pembrolizumab.
- The OS is defined as the time from the first dose of treatment until death by any cause or the last date the patient was known to be alive. Patients who are lost to follow-up and the patients who are alive at the date of data cut-off will be censored at the date the patient was last known alive (censoring rules are specified in Table 3 - Appendix I).

A Kaplan-Meier survival analysis will be carried out to analyse PFS and OS. Number of events, median survival time and the corresponding 95% CI will be provided. Survival curves will be reported.

- The ORR is defined as the number of patients with CR and PR divided by the number of patients in the analysis population. Tumor response will be defined as best response, based on local investigator's assessment according to RECIST v.1.1. ORR will be reported as a proportion with the corresponding 95% CI.

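### SAP Appendix I censors PFS at treatment discontinuation without requiring that no event followed, and censors deaths after the end of treatment visit, contrary to protocol 6.4.3 and SAP 6.2.1

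*SAP*

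**What the plan says.** **Protocol 6.4.3** gives this definition of PFS: "the time from first dose of study treatment to the first documented disease progression based on RECIST v.1.1 or death due to any cause". The earlier of the two counts. Stopping treatment is not mentioned as a reason to censor.

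**SAP 6.2.1** uses the same event and states who is censored: "Patients with no progression or death will be censored at the date of their last evaluable imaging". SAP 6.9 also measures time to progression or death.

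**SAP Appendix I** adds a separate situation, "Treatment discontinuation for toxicity or other reason", to Table 1 (radiological PFS) and Table 2 (investigator PFS). The outcome is Censored in both. The date is the last imaging of the measured lesions in Table 1 and the last adequately assessed visit in Table 2. A footnote to the row in Table 1 adds that "death after the end of treatment visit will be considered as censored with the date of last radiological assessment of measured lesions". Table 2 has a matching footnote.

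**Follow-up after stopping.** For patients who stop without progression, the second note in protocol 6.4.4 says "every effort should be made to continue monitoring their disease status by tumor imaging". Footnote 4 of protocol Appendix 1 repeats this, then leaves tumor evaluation during the suspension of the First Course to the investigator and local practice. The protocol synopsis, 3.1 and 6.4.1 instead list treatment discontinuation among the points at which scheduled imaging ends. For candidates for the Second Course, protocol 6.2 states: "A eCRF page will have to be completed in order to confirm the progression date".

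**The concern.** The protocol endpoint is time to progression or death, whether or not the patient is still on treatment. If the discontinuation row is applied as written, the SAP estimates something nearer to PFS while on treatment. Events that were scanned and recorded would not count.

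Protocol 8.4 accepts Kaplan-Meier censoring only if dropping out is unrelated to prognosis. That is doubtful for patients who stop because of toxicity.

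There is also a problem of reproducibility. One programmer working from SAP 6.2.1 and another working from Appendix I could report different PFS results from the same database, and a SAP should rule that out.

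**Working it through.** **1. The plan's own figures.** The documents give no event count, power or precision for PFS. The only sample-size figure is for the clinical benefit rate (protocol 8.1), and it reproduces. For at least 17 of 39, exact binomial:
- P(X ≥ 17 | 39, 0.30) = 0.04998, against a stated alpha of 0.05.
- P(X ≥ 17 | 39, 0.50) = 0.832, against a stated power of 80%.
- 39 / 0.90 = 43.3, rounded up to 44.

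None of these depends on PFS censoring.

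**2. One patient traced through the rules.** Take a patient who stops for toxicity between the week 18 and week 27 scans without progression. In case A the week 27 scan shows RECIST progression. In case B she dies after the end of treatment visit, with no progression and no missed assessments.

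| Source | Case A | Case B |
|---|---|---|
| Protocol 6.4.3 | Event | Event |
| SAP 6.2.1 | Event | Event |
| Appendix I, progression or death rows | Event | Event |
| Appendix I, discontinuation row | Censored | Censored |
| Appendix I, footnotes | Not addressed | Censored, explicitly |

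Case A has two answers because no row takes precedence. Reading the last imaging date as including scans after stopping does not help, since the outcome is still Censored.

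**3. Which reading is likelier.** Table 1 already has a row for patients with no progression, with the same date and outcome. For a patient who stops and has no later event, the discontinuation row is therefore redundant. It changes a result only by removing an event, and its footnote does exactly that for deaths.

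**4. Check against duration of response.** For DoR, SAP 6.2.1 censors only patients without progression or death. A responder who stops for toxicity and later progresses is thus a DoR event, yet can be censored for PFS.

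**5. Size in events.** Upper bound = 44 × share stopping before documented progression. The shares are assumptions.

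| Share | 5% | 10% | 20% | 30% |
|---|---|---|---|---|
| Events lost, at most | 2.2 | 4.4 | 8.8 | 13.2 |

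**6. Size in the median.** Large-sample simulation with exponential PFS. The on-treatment median m is 4.1 months (eribulin arm of the second phase III trial, protocol 1.3.3), h = ln 2 / m, and the stopping hazard is h × share / (1 − share). The progression hazard after stopping is 1, 1.5 or 2 times h (assumed). Medians in months:

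| Share, hazard after stopping | All events counted | Censored at stopping | Censored at last scan |
|---|---|---|---|
| 20%, ×1 | 4.10 | 4.10 | 3.94 |
| 20%, ×1.5 | 3.94 | 4.08 | 3.92 |
| 20%, ×2 | 3.84 | 4.08 | 3.92 |
| 30%, ×1 | 4.10 | 4.10 | 3.82 |
| 30%, ×1.5 | 3.88 | 4.11 | 3.83 |
| 30%, ×2 | 3.71 | 4.09 | 3.80 |

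Compared with counting all events, the shift runs from 3.82 − 4.10 = −0.28 to 4.09 − 3.71 = +0.38 month. With m = 3.7 (first phase III trial) and 30% stopping, it runs from 3.40 − 3.70 = −0.30 to 3.70 − 3.35 = +0.35. Progression times are continuous here, which is why back-dating to the last scan can lower the median.

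**7. Size in the 6-month rate.** When progression is detected only at 9-week scans (median 4 months, 10% to 25% stopping), PFS at 6.3 months is about 0.34 under the table rule and 0.30 to 0.34 when all events count. The gap is nil at hazard ×1 and about 1 to 4 points at ×1.5 to ×2. For comparison, the 95% half-width for a rate of 0.32 in 44 patients is 1.96 × √(0.32 × 0.68 / 44) = 0.138, or about 14 points.

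**The case against.** The strongest reply is that the tables do not clearly discard progressions. Their progression rows are not confined to time on treatment, the footnotes speak only of deaths, and a programmer who follows SAP 6.2.1 would count the event. This stands as far as it goes: for progressions, loss is the likelier reading but not a certain one. It does not rescue the deaths, and it concedes that the result depends on the reader.

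The data may also be thin. Three places in the protocol end scheduled imaging at discontinuation. The progression-date page is required only for Second Course candidates. Many patients who stop will start another therapy, which ends imaging under protocol 6.4.4 and is a censoring reason in Table 2. All of this stands, so the event losses are upper bounds.

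The SAP says its censoring follows a 2007 regulatory guidance, so the row may be a deliberate convention. That source cannot be checked from the documents, and citing it does not remove the conflict with SAP 6.2.1 and the protocol.

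A reader might also infer a larger problem from the SAP synopsis, which says "No maximum duration of treatment is specified" while the protocol now caps pembrolizumab at 35 doses: planned completers would be censored and the progression that opens the Second Course lost. The documents do not support giving this weight. Dose 35 falls 34 × 21 = 714 days, or 23.5 months, after the first dose. With exponential PFS, 0.5^(23.5/3.7) = 1.2% and 0.5^(23.5/4.1) = 1.9% are still progression-free, which is 0.5 to 0.8 of 44 patients. A longer median on the combination would raise this. However, patients may continue eribulin alone after dose 35, so treating them as discontinued is itself an inference.

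**Conclusion.** The conflict is real and rests on the text, not on the simulations. Appendix I censors at discontinuation without a condition. Protocol 6.4.3 and SAP 6.2.1 do not. Deaths after the end of treatment visit are dropped explicitly; recorded progressions after stopping can be dropped, depending on which row is applied.

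The effect is modest: at most about 4 of 44 events if 10% stop first and about 9 if 20% do, with a median shift of a few tenths of a month at most. These figures rest on assumed stopping rates, exponential times and assumed hazards after stopping. A reader might infer that the rule always flatters PFS. It does so if patients who stop progress faster than those still on treatment, but back-dating can offset or reverse this, so the direction is not fixed.

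The scope is secondary PFS, overall and in PD-L1 positive tumors. The matter should be corrected before analysis, but it does not threaten the trial's primary conclusion.

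**What to change.** In SAP Appendix I, Tables 1 and 2:

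- Limit the discontinuation row to patients with no progression or death documented afterwards.
- Count RECIST progressions documented on scans after stopping, at the date that each table's progression rows assign.
- Amend both footnotes so that deaths after the end of treatment visit are events unless another stated censoring rule applies, such as two or more missed assessments.
- State which row prevails when more than one fits.
- Add to Table 1 the new-anticancer-treatment row that Table 2 already has. Deleting the discontinuation row outright would be worse, because Table 1 could then count progressions that occur on later therapy.
- Keep the present rule as a labelled sensitivity analysis.

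In the protocol, reconcile the synopsis, 3.1 and 6.4.1 (scheduled imaging ends at discontinuation) with the 6.4.4 note and Appendix 1 footnote 4 (imaging continues).

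The cost is table wording, a protocol clarification and one extra analysis run. The downside is that PFS may look slightly shorter.

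### For a progression-free death after the end-of-treatment visit with at most one missed assessment, the SAP's PFS tables say event in the rows and censored in the footnotes

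*SAP*

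**What the plan says.** SAP Appendix I sets censoring rules for radiological PFS (Table 1) and for PFS as assessed by the investigator (Table 2).

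- **Death rows, both tables.** "Death before first progression disease assessment" and "Death between adequate assessment visits" count as events on the date of death. Neither row carries a footnote mark.
- **Missed-assessment rows.** Table 1 censors "Death or progression after more than one missed visit". Table 2 censors a death that follows two or more missed assessments.
- **Footnotes.** They are marked on the missed-assessment row and on "Treatment discontinuation for toxicity or other reason". In Table 1, "death after the end of treatment visit will be considered as censored with the date of last radiological assessment of measured lesions". In Table 2, "death after the end of treatment visit will be considered as censored with the date of last adequate assessment". Neither sets a condition on missed assessments.
- **Table 2 only.** "New anticancer treatment started with no claim of progression" is a further censoring row.
- **Definitions.** Protocol 6.4.3, SAP 6.2.1 and SAP 6.9 all count death as a PFS event. SAP 6.2.1 censors only patients with neither progression nor death, and says the rules follow a 2007 FDA guidance.

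**The concern.** For a death after the end-of-treatment (EOT) visit with no more than one missed assessment, the row and the footnote give opposite outcomes. The SAP does not say which prevails, so two analysts could code the same death differently. Most such deaths should reach the database, because Protocol 3.3.4 collects survival status 12 months after the last dose.

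The footnote answer is also statistically the worse one. It censors a patient because she died. Protocol 8.4 rests the Kaplan-Meier analysis on drop-out being unrelated to prognosis, which cannot hold here, and the result is a higher PFS.

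It also splits PFS from duration of response. SAP 6.2.1 ends response at death from any cause, so a responder's post-EOT death would be an event for one endpoint and censored for the other. The rule feeds both PFS versions and the ten subgroup tables listed for each.

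**Working it through.** **1. Where row and footnote disagree.** Inputs: EOT visit within 30 days of the last dose (Protocol 3.3.3); scans every 9 weeks, that is 63 days, in year 1 (Protocol 6.4.1); screening on days -28 to -1 (Protocol Appendix 1). Days are from first dose, and no new therapy has started.

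| Patient | Missed scans | Rows | Footnote |
|---|---|---|---|
| A: last dose day 8, EOT by 8 + 30 = day 38, dies day 50, first scan due day 63 | 0 | Event, day 50 | Censored at the screening scan, before time zero |
| B: clear scan day 126, last dose day 127, EOT by day 157, dies day 170, next scan due day 189 | 0 | Event, day 170 | Censored, day 126 |
| C: as B, day-189 scan missed, dies day 220 | 1 | Event, day 220 | Censored, day 126 |
| D: as B, scans on days 189 and 252 missed, dies day 260 | 2 | Censored, day 126 | Censored, day 126 |

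The clash is confined to zero or one missed assessment. Deaths after documented progression are unaffected.

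**2. Effect per recoded death.** The documents do not give the number of such deaths, so this is an illustration. Assumptions: N = 44; exponential PFS with median 4.1 months (the eribulin figure from study 301, Protocol 1.3.3); 9-weekly scans. In 6,000 replicates, k deaths falling between week 5 and week 27.4 were recoded as censored at the previous scan.

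- Rise in PFS at 6.3 months, k = 1: +1.28 points (5th-95th percentile 0.69-1.91).
- k = 2: +2.56 points (1.58-3.60).
- One death before the first scan, censored at time zero (patient A): +0.80 points (0.53-1.06).
- At 12 months, k = 1: about +0.6 points.
- Kaplan-Meier median, exact scan dates: unchanged in 86% of replicates for k = 1 and 75% for k = 2.

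**3. Range over scenarios.** 300,000 patients per scenario; 10% or 20% stop without documented progression; hazard after stopping is 0.7 to 3 times the on-treatment hazard. The death share of first events after stopping is varied. Where scans end at the stop, scans not done count as missed. Rise in PFS at 6.3 months from following the footnote, in points:

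| Death share | EOT day 30, scans continue | EOT day 30, scans end | EOT day 7, scans continue | EOT day 7, scans end |
|---|---|---|---|---|
| 5% | 0.04-0.16 | 0.02-0.11 | 0.07-0.25 | 0.04-0.20 |
| 10% | 0.11-0.34 | 0.05-0.22 | 0.13-0.49 | 0.08-0.40 |
| 26% | 0.26-0.87 | 0.11-0.51 | 0.35-1.31 | 0.18-1.04 |
| 50% | 0.52-1.67 | 0.22-0.93 | 0.68-2.56 | 0.35-1.90 |
| 100% | 1.06-3.51 | 0.42-1.68 | 1.34-5.53 | 0.66-3.52 |

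The 26% row matches 4.1/15.9 = 0.26, the ratio of median PFS to median OS for eribulin in study 301; it is only a rough guide. Expected affected deaths before 6.3 months among 44 patients: 0.02 to 2.6 (EOT day 30) or 0.04 to 4.4 (EOT day 7).

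**4. Yardstick.** PFS at 6.3 months under the definition was 0.29 to 0.37 in these scenarios. Binomial standard error = √[p(1 − p)/44]: √(0.32 × 0.68/44) = 0.070 and √(0.35 × 0.65/44) = 0.072, so about 7 points.

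**The case against.** The best defence is that the footnotes are the only text naming deaths after EOT, both say censored, and a specific rule beats a general one. On that reading only a precedence clause is missing. This does not carry. The footnotes present themselves as a consequence of the criteria, not as an exception, and are marked only on rows that already censor. SAP 6.2.1 also sides with the death rows. If the footnotes are instead confined to their marked rows, the clash remains: a patient who stops for toxicity and dies before her next scan meets both the discontinuation row and a death row. That reading does narrow Table 1, where the row for discontinuation with undocumented progression is unmarked. The cited FDA guidance is not available here, and citing it does not say which of the SAP's own statements applies.

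Second, patients B and C need a scan scheduled after treatment stops. The protocol synopsis, 3.1 and 6.4.1 end imaging at discontinuation; the note in 6.4.4 and Appendix 1 footnote 4 ask for it to continue. This is fair, but patient A needs no later imaging, although so early a death should be uncommon.

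Third, PFS at 6.3 months is not a planned output. SAP 6.2 plans the median and 1- and 2-year rates, on which one recoded death usually does less. The largest table values need every first event after stopping to be a death at triple hazard. Some deaths may also go unrecorded through withdrawal or early termination by the sponsor. These points stand, and they limit the size of the effect without removing the contradiction.

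**Conclusion.** The two PFS tables are wrong as written: one class of death has two codings and no stated precedence. The contradiction follows from the text alone and rests on no assumption. In Table 2 it is clearest when no new anticancer treatment has started, since that has its own censoring row.

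The numerical effect is probably small against sampling error. Its size depends on the assumed 4.1-month median, the share of patients who stop without progression, the hazard after stopping and the share of deaths, which the documents do not supply for this combination. PFS is a secondary endpoint; the 17-of-39 CBR rule, the sample of 44 and OS do not change. It should be fixed before database lock, because a choice made afterwards could depend on the results.

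**What to change.** 1. Delete the post-EOT death footnotes from Tables 1 and 2. This restores the SAP's own definition.
2. State that the discontinuation rows censor only patients with no later qualifying progression or death. A documented progression (in Table 2 also an investigator's claim) or a death is then an event regardless of discontinuation, except under the existing missed-assessment rows and, in Table 2, the new-treatment row.
3. If censoring of post-EOT deaths is wanted as a sensitivity analysis, define it explicitly: censor progression-free deaths after EOT at the last assessment, or at first dose if there is no post-baseline assessment, with this rule overriding both death rows.
4. In Table 2, replace the reference to randomization with first dose; all patients receive the same treatment and none is randomized.
5. Reconcile the protocol passages on imaging after discontinuation, including the sentence in Appendix 1 footnote 4 that leaves evaluation to local practice between and during courses. State in the SAP whether scans not done after discontinuation count as missed.

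Items 1 to 4 cost SAP edits and perhaps a slightly shorter reported PFS. The death rule needs no new data, because deaths are collected for OS. Item 5 could require further scans, depending on how it is resolved.
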